7.4 Overdose

An overdose is defined as a known deliberate or accidental administration of IMP to or by a subject, at a dose greater than 110% of the dosage assigned to that individual subject according to the trial protocol.

All cases of overdose (with or without associated AEs) will be documented in the eCRF. Cases of overdose without manifested signs or symptoms are not considered AEs. AEs associated with an overdose will be documented in the eCRF.

SAEs associated with overdose should be reported according to the procedure outlined in Section 7.7.

In the event of overdose, the subject should be treated symptomatically.

7.5 Adverse Event Assessment Definitions

7.5.1 Severity

The investigator should assess the severity of all AEs according to the following definitions:

- **Mild:** A type of AE that is usually transient and may require only minimal treatment or therapeutic intervention. The event does not generally interfere with usual activities of daily living.
- **Moderate:** A type of AE that is usually alleviated with specific therapeutic intervention. The event interferes with usual activities of daily living, causing discomfort but poses no significant or permanent risk of harm to the research subject.
- **Severe:** A type of AE that interrupts usual activities of daily living, or significantly affects clinical status, or may require intensive therapeutic intervention.

For reporting of (S)AE related laboratory abnormalities, the severity (intensity) needs to be evaluated by the investigator in the accordance with the defined criteria for assessment of laboratory value abnormalities, following the CTCAE criteria (version 5, November 2017) (the investigator will be requested to provide the values for severity grades.).

Note the distinction between seriousness and severity: the term severe is used to describe the intensity of the event and a severe event is not necessarily serious (e.g. a severe headache would probably not constitute an SAE; however, a mild myocardial infarction could constitute an SAE). The seriousness criteria serve as a guide for defining regulatory reporting obligations.

If an AE changes severity over time, a new AE has to be reported with the new severity.

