7.6 Reporting of Adverse Events

All events meeting the definition of an AE must be reported from signing of the main ICF onwards until the last trial visit. Only medically qualified personnel (investigators) must assess AEs.

AEs must be reported by the investigator in the source data and the eCRF. The diagnosis will be recorded, if available and applicable. If no diagnosis is available, each sign and symptom will be recorded as individual AEs in the eCRF.

Recurring AEs with fluctuations in severity should be reported separately, i.e. with separate start date and time and stop date and time. Recurring AEs for which the severity is stable, could be reported as intermittent AEs, with the start date being the start of the first episode of the AE. If the severity changes, the intermittent AE should get a stop date, and a new AE with the new severity should be reported.

Investigators will receive copies of initial and follow-up expedited safety reports (unexpected SAEs that are determined to be associated with the use of IMP) from the sponsor or designee. The investigator is responsible for fulfilling applicable local reporting requirements to their IEC/IRB. Investigators must forward copies of the IEC/IRB notification to the sponsor or designee. In the European Union (EU), the sponsor or designee is responsible for notifying the European Medicines Agency (EMA), IEC/IRB, and competent authorities. In regions/countries other than the EU, reporting of events to IEC/IRB or local authorities will be performed by the investigator/sponsor or designee and in accordance with local procedures/regulations.

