### 3 ENDPOINTS

#### 3.1 Primary Endpoint

- Comparison of adverse event (AE, SAE, AESI) frequency and severity by dose (cohort), for single and multiple administration, and by mutated gene (subcohort) and overall using the Safety Analysis Set following 12 weeks of MAD treatment and after 24 weeks of MAD treatment (12 weeks in the MAD part + 12 weeks in the MAD extension part; Week 25 visit) or discontinued earlier.

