### **6.14.1 Adverse Events**

Adverse events will be reported separately for SAD and MAD + MAD Extension parts.

A pre-therapy AE is defined as any AE that starts before the first dose of study drug.

A treatment emergent adverse event (TEAE) is defined as:

- Any AE that has an onset on or after the first dose of study drug and before last dose of study drug + 28 days.
- Any pre-existing AE that has worsened in severity on or after the first dose of study drug and before the last dose of study drug + 28 days.

A treatment-related AE is defined as an AE as being related to the study drug. If an AE has missing relationship it is assumed to be related to the study drug for analysis purposes.

Maximum severity will be assumed for an AE with missing severity.

The following tables will be presented for AEs:

- Summary of All Adverse Events, incidence and the number of events.
- Pre-therapy AEs by system organ class and preferred term, incidence and number of events
- TEAEs by system organ class and preferred term, incidence and number of events
- Treatment-related TEAEs by system organ class and preferred term, incidence and number of events

- Serious TEAEs by system organ class and preferred term, incidence and number of events
- TEAEs leading to treatment withdrawal by system organ class and preferred term, incidence and number of events
- All AEs of special interest by system organ class and preferred term, incidence and number of events
- TEAEs by system organ class, preferred term and maximum severity, incidence
- Treatment related TEAEs by system organ class, preferred term and maximum severity, incidence
- TEAEs by system organ class, preferred term and study drug relationship, incidence
- Listing of Deaths (presented in the Table section of the appendices)
- Listing of Serious TEAEs (presented in the Table section of the appendices)

All AEs will be listed.

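### The AE number-of-events columns count records rather than episodes, and a record that spans the first dose can be wrongly counted as treatment-emergent or wrongly left out.

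*Protocol*

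**What the plan says.** The primary endpoint in SAP 3.1 begins "Comparison of adverse event (AE, SAE, AESI) frequency and severity by dose (cohort" and continues by single or multiple administration and by mutated gene; Protocol 3.3.1 matches it. Neither document says whether frequency means subjects, episodes or records.

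The recording rules are in the protocol:

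- Section 7.5.1: "If an AE changes severity over time, a new AE has to be reported with the new severity". No direction of change is given.
- Section 7.6, stable recurrences: "Recurring AEs for which the severity is stable, could be reported as intermittent AEs, with the start date being the start of the first episode". Merging is optional.
- Section 7.6, when a merged event changes: "If the severity changes, the intermittent AE should get a stop date, and a new AE with the new severity should be reported".
- Section 7.6, fluctuating recurrences: "Recurring AEs with fluctuations in severity should be reported separately, i.e. with separate start date and time and stop date and time".

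SAP 6.14.1 has two routes to a treatment-emergent AE, each running to 28 days after the last dose. The first is "Any AE that has an onset on or after the first dose of study drug". The second is "Any pre-existing AE that has worsened in severity on or after the first dose of study drug". The same section tabulates both subject incidence and number of events for TEAEs, treatment-related TEAEs, serious TEAEs, TEAEs leading to withdrawal and AEs of special interest. The severity and relationship breakdowns give incidence only. SAD is reported separately from MAD plus extension. There is no rule for linking records, for a pre-dose AE that eases, or for assigning an AE to a part.

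**The concern.** The two protocol rules push the record count in opposite directions. A severity change splits one episode into several records, and the merging option can turn several episodes into one. A difference between dose levels in number of events could then reflect how much severity fluctuated, or how a site chose to record, rather than how often events occurred.

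The second problem concerns classification. The second TEAE bullet shows that a pre-existing AE was meant to count only if it worsened. The first bullet tests only the onset date of the record, so a new record opened because an AE eased can qualify on its own.

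The matter is still live. The study was terminated, but SAP 8 keeps the full safety analyses in the abbreviated report, and the AE tables remain in the SAP 12 list.

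**Working it through.** The documents give no AE rate or event count to reproduce. The check applies the written rules to small invented histories; these are illustrations, not expected rates.

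**Inputs.** Recording rules: Protocol 7.5.1 and 7.6. TEAE rules: SAP 6.14.1. First dose is Day 1. The new record is assumed to start on the day severity changes. Group sizes are the targets in SAP 4: up to 3 subjects with an *MTM1* mutation per dose level, about 6 subjects per dose level, and 18 overall.

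| History in one subject | TEAE records | Subjects with a TEAE |
|---|---|---|
| A. One post-dose episode, mild, moderate, mild | 3 as written; 1 if linked | 1 either way; maximum severity moderate either way |
| B. Four mild post-dose recurrences | 1 if merged; 4 if separate | 1 either way |
| C. Moderate AE before dosing, eases to mild on Day 10 | 1 as written; 0 if only worsening counts | 1 as written; 0 if only worsening counts |
| D. Mild AE before dosing, recurs at the same severity on Day 10 | 0 if merged; 1 if separate | 0 if merged; 1 if separate |

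A and B scale simply. A laboratory AE passing through grades 1, 2, 3, 2, 1 gives 5 records for one episode. A mild headache after each of 24 weekly infusions is 1 event or 24. Each remains one subject.

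In C, the new record has a post-dose onset and meets the first bullet, although nothing worsened. In D, the merged record keeps the start date of its first episode, so it is a pre-therapy AE under SAP 6.14.1. It fails the first bullet on date and the second because severity is unchanged.

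**Effect of one misclassified subject on incidence**, 100 / n percentage points:

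- n = 3: 100 / 3 = 33.3
- n = 6: 100 / 6 = 16.7
- n = 18: 100 / 18 = 5.6

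**SAD and MAD.** If an AE is assigned to a part by record onset, C and D repeat at the first MAD dose. An AE from the SAD part that only eases during MAD would become a MAD event.

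**The case against.** The strongest reply is that the main safety reading does not rest on event counts. Protocol 9.8 and SAP 6.14.1 report the incidence of subjects beside the number of events, and the severity tables use maximum severity per subject. Histories A and B leave both unchanged. This stands. A reader might infer that the primary endpoint as a whole counts records; the documents do not support that.

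A reader might also infer that any long-standing symptom that eases on treatment becomes a TEAE. Protocol 7.1 rules that out: anticipated fluctuations of conditions present at the start that do not worsen are not AEs, and illness found at screening is medical history unless it worsens or becomes serious. What remains is an AE that arose after consent and was ongoing at first dose. Such AEs are foreseeable, since collection starts at the main consent (Protocol 6.2.2.1), run-in visits can repeat every 12 weeks (6.1.2), and the SAP plans a pre-therapy AE table.

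Nor do the documents support a claim that incidence is simply inflated, since history D lowers it. The SAD/MAD effect is not established either: the SAP states no assignment rule, and the AE would have to be ongoing at the start of MAD, at least 16 weeks after the SAD dose (4 weeks of follow-up plus at least 12 of washout). Protocol 7.5.1 also gives no start date for the new record of a non-recurring AE, so a post-dose onset there is an inference, though the natural one.

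Finally, no hypothesis is tested, all AEs are listed, and the trial pausing rules in Protocol 7.11.1 turn on individual events. These facts limit the consequence but do not correct the tables.

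**Conclusion.** The point holds in a limited form. All number-of-events columns in SAP 6.14.1 are record counts, and they depend partly on an optional site practice. Subject incidence and maximum severity are sound for records that all start after dosing within one part.

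Incidence can be wrong in either direction only where records span the first dose, or the first MAD dose if assignment is by record onset. The size is one subject at a time: 33.3 points in a sub-cohort of 3, 16.7 in a cohort of 6, and 5.6 in 18. How many subjects would be affected cannot be derived from the documents. The easing case assumes that the new record is dated at the severity change; the drop-out case assumes that the site used the merging option. The correction is worth making because the written TEAE rule contradicts its own evident intent and costs little to repair.

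**What to change.** Amend SAP 6.14.1 only:

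1. State that a record opened solely because severity decreased, for an AE that began before the first dose (for the MAD tables, before the first MAD dose), is not treatment-emergent for that part.
2. For event counts, link contiguous records of the same preferred term in one subject within the same part into one event, at the maximum severity reached in that part. Keep any worsening on or after the first dose of a part as an event of that part. Without this exception, an AE that was mild in SAD and became severe in MAD would be moved back to its SAD onset, although the MAD dose may differ.
3. Name subject incidence as the main measure of AE frequency, and flag intermittent AEs that span the first dose.

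Keep every record in the listings. A change to Protocol 7.6 is not worth making now that the study has been terminated: it could not separate recurrences already merged. Linking cannot undo that merging either, which is a further reason to lead with subject incidence.

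The cost is SAP wording, a small programming step on the AE start and stop dates, and slightly lower event counts.

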7.5.2 Relationship to Investigational Medicinal Product

The investigator must assess the causal relationship of the IMP for each (S)AE. The investigator should decide whether, in his or her medical judgment, a possibility exists that the event may have been caused by the IMP. If there is a valid reason, even if undetermined or untested, for suspecting a cause-and-effect relationship between the IMP and the occurrence of the AE, then the AE should be considered 'related'. If there is no valid reason for suggesting a relationship, i.e. when a relationship to IMP is excluded, then the AE should be classified as 'not related'. The causality assessment must be documented in the source document.

The following additional guidance may be helpful:

Term	Relationship	Definition
Related	Yes	As a therapeutic dose has not yet been established for the IMP, at this time, all noxious and unintended responses to the IMP are considered to be related to the IMP unless they are reasonably attributed to another cause. There is a temporal relationship between the event and the administration of the IMP.
Not Related	No	The event can be readily explained by other factors such as the concomitant therapy or accident and no plausible temporal or biologic relationship exists between the IMP and the event. In addition, this assessment can be used in cases where the subject did not receive any treatment with IMP.

7.6 Reporting of Adverse Events

All events meeting the definition of an AE must be reported from signing of the main ICF onwards until the last trial visit. Only medically qualified personnel (investigators) must assess AEs.

AEs must be reported by the investigator in the source data and the eCRF. The diagnosis will be recorded, if available and applicable. If no diagnosis is available, each sign and symptom will be recorded as individual AEs in the eCRF.

Recurring AEs with fluctuations in severity should be reported separately, i.e. with separate start date and time and stop date and time. Recurring AEs for which the severity is stable, could be reported as intermittent AEs, with the start date being the start of the first episode of the AE. If the severity changes, the intermittent AE should get a stop date, and a new AE with the new severity should be reported.

Investigators will receive copies of initial and follow-up expedited safety reports (unexpected SAEs that are determined to be associated with the use of IMP) from the sponsor or designee. The investigator is responsible for fulfilling applicable local reporting requirements to their IEC/IRB. Investigators must forward copies of the IEC/IRB notification to the sponsor or designee. In the European Union (EU), the sponsor or designee is responsible for notifying the European Medicines Agency (EMA), IEC/IRB, and competent authorities. In regions/countries other than the EU, reporting of events to IEC/IRB or local authorities will be performed by the investigator/sponsor or designee and in accordance with local procedures/regulations.

7.7 Prompt Reporting of Serious Adverse Events

All events meeting the definition of an SAE must be reported from signing of the main ICF onwards until the last trial visit. SAEs must be reported immediately to the sponsor as soon as the investigator determines that the event meets the protocol definition for that event. Further details will be described in the site manuals (e.g. Site Cohort Management Manual, Site Operations Manual).

The information will be reported on the SAE eCRF and will include assessment of seriousness, severity, causal relationship to the IMP or trial procedures, outcome, and a narrative description of the course of the event. Additional information may be subsequently provided.

All SAEs, regardless of causality, must be reported to the sponsor or designee (the contract research organization [CRO] responsible for Pharmacovigilance) within 24 hours of the first awareness of the event in the eCRF. In the event the eCRF system is unavailable, a paper back-up SAE form should be completed and submitted (see Emergency Contact Information).

All relevant documents including but not limited to diagnostic procedures, hospital records, autopsy reports after redaction of all subject identification details must be faxed or e-mailed (see Emergency Contact Information).

SAEs occurring in a subject after the subject has completed the clinical trial and for which a reasonable possibility of a causal relationship is assessed by the investigator should be reported by the investigator to the sponsor, if the investigator becomes aware of them regardless of the time that has elapsed (post-trial events).

7.8 Regulatory Reporting Requirements for Serious Adverse Events and Other Events

Prompt notification of SAEs by the investigator to the sponsor is essential, so that legal obligations and ethical responsibilities towards the safety of subjects are met. This is particularly true for this trial as this involves the first use of DYN101 in humans; safety concerns drive the Pausing/Stopping rules for the trial (Section 7.11.1). Further details will be described in the site manuals (e.g. Site Cohort Management Manual, Site Operations Manual).

The sponsor has a legal responsibility to notify both the local regulatory authority and other regulatory agencies about the safety of a product under clinical investigation. The sponsor will comply with the ICH/EMA and country-specific regulatory requirements relating to safety reporting to the regulatory authority, IEC/IRB, and investigators.

Expedited reporting of SUSARs will be taking place within 7 or 15 days depending on fatal/life threatening status, seriousness, expectedness, and causality from all clinical trials globally (SUSAR reporting in EU). Any suspected adverse reaction that is both serious and unexpected according to the IB will be reported provided there is evidence to suggest a causal relationship between the IMP and the AE.

Relevant follow-up information to a SUSAR will be submitted as soon as the information is available.

Information about SUSARs is also forwarded to the investigators and IEC/IRB. Additionally, safety information will be forwarded to Ionis Pharmaceuticals, Inc, owner of DYN101.

An investigator who receives a SUSAR describing (an) SAE(s) or other specific safety information (e.g. summary or listing of SAEs) from the sponsor will file it with the IB, and will notify the IEC/IRB, if appropriate according to local requirements.

In addition to submission of SAEs, an annual development safety update report will be prepared and submitted to the EMA (and locally, if applicable), according to the development international birth date.

7.9 Reporting of Pregnancies

Should a pregnancy occur in a female subject or female partner of a male subject, it will be recorded separately from AEs, but will be reported by the investigator in a manner identical to the reporting of SAEs (see Section 7.7), by completing the pregnancy eCRF.

All attempts will be made to follow the pregnancy until the outcome of the pregnancy has been determined, and to capture information on the development of the infant in the period up till and including the age of 1 year. This information will only be collected if separate informed consent is given by the subject and the subject's sexual partner.

Any report of a congenital abnormality/birth defect is an SAE and should be reported as such. Any complication of a pregnancy occurring during this trial, including elective termination for medical reasons, must be reported in the pregnancy eCRF.

In the event the eCRF system is unavailable, a paper back-up SAE form should be completed and submitted (see Emergency Contact Information).

7.10 Follow-up on Adverse Events

All AEs and SAEs should be followed until stable, resolved or they have reached a "final outcome" or the subject's participation in the trial ends, whichever comes first.

Adverse events assessed as "related" to IMP and all SAEs and AEs of special interest (regardless of their relationship to IMP) still ongoing after the end of trial participation (i.e. after the follow-up call) should be followed on a regular basis according to the investigator's clinical judgment until the condition is stable.

The outcome "recovering" can be used as the "final outcome" for events that are stabilized (i.e. no further worsening is expected) and expected by the investigator to resolve over time.

The outcome "not recovered" can be used as the "final outcome" for events that are not expected to resolve over time (e.g. cancer).

The outcome "unknown" can be used as the "final outcome" for events for which the outcome is not known.

If a subject dies during the reporting period, attempts should be made to obtain muscle biopsy material to assess muscle histology, ASO concentration, and *DNM2* mRNA.

Follow-up information received after the end of the trial should be sent to the sponsor.

7.11 Pausing/Stopping Rules

7.11.1 Pausing/Stopping Rules for the Trial

The investigators, together with the medical monitor, will be responsible for the safety monitoring of the trial, and will pause IMP administration in case any of the pre-specified pausing/stopping rules have been met. The sponsor's medical lead will be involved in all discussions and decisions.

If any of the following events occur in any subject in any cohort who received at least one IMP administration in the trial (at any site), the investigator will pause the IMP administration of further subjects in all cohorts and will notify the medical monitor immediately. The medical monitor will inform all the other investigators to pause further IMP administration as well and will notify the IDMC immediately.

- Death in any subject, considered related to IMP; OR
- An anaphylactic reaction within 24 hours of the start of the infusion or the presence of generalized urticaria within 72 hours of the start of the infusion in any subject, considered related to IMP; OR
- An SAE in any subject, considered related to IMP.

Events which would not meet the hospitalization criterion to be reported as an SAE for this trial are:

- Overnight stay for convenience based on the subject/caregiver personal choice
- Overnight stay offered by the investigator based on non-clinical grounds
- For observation of minor reactions which would not on their own warrant admission to hospital, but is preferred in this vulnerable population; OR
- ALT or AST $> 8 \times$ ULN, considered related to IMP and confirmed by repeat testing.

Subjects experiencing any of the events defined above will be permanently withdrawn from IMP administration and will discontinue the trial (see Section 4.5).

Within 3 business days, the IDMC will convene to review the available safety data as outlined in the charter and to discuss further actions (e.g. continue either as planned or with modifications, or to stop the trial). In the event a stopping rule is met, the national authorities will be informed through a substantial amendment. The sites will be allowed to resume activities after the national authorities have received, reviewed, and approved the available safety data and any protocol amendment, if any, and upon receipt of a written notification from the sponsor to allow continued treatment and enrollment.

In case the pause is lifted, withdrawn subjects can be replaced to maintain full enrollment within the sub-cohort under the circumstances described in Section 3.1.2.

Subjects who were awaiting the start of their cohort and whose screening period is longer than the protocol-defined 6 weeks as a result of a pause in IMP administrations will be allowed to be re-screened in line with the re-screening procedures outlined in Section 6.1.1.

